## 7.6 Preclinical Evidence for Synergy of PLX3397 with Radiation

Just as macrophages support tumor growth, invasion and metastasis in non-CNS cancers, microglial cells have been shown to support the growth and invasion of glioblastomas (Markovic 2009). This supportive role relies on a paracrine system in which the glioblastoma cells attract microglial cells (presumably by secreting CSF-1) and the microglial cells secrete growth factors such as EGF which stimulate glioblastoma migration. To explore its therapeutic potential in glioblastoma, PLX3397 was tested in an orthotopic tumor model in which 9L Fisher glioblastoma cells are implanted intracranially to syngeneic rats. As shown in Figure 2, PLX3397 inhibits the growth of the 9L tumors when dosed for 10 days using a chow formulation (nominal dose of 80 mg/kg). Tumor growth was determined using volumetric MRI.

[figure not shown]
**Figure 2: PLX3397 Inhibits Intracranial Tumor Growth in the 9L Fisher Glioblastoma Rat Model**

In an additional glioblastoma model it was demonstrated that co-cultured microglial cells enable invasion of GL261 glioblastoma cells in a manner that depends on both Fms and the epidermal growth factor (EGF) receptor (Coniglio 2012). Thus, both PLX3397 and erlotinib block invasion in this co-culture assay. Pharmacology studies demonstrate that the microglia depend on CSF-1 (secreted by the GL261 cells) and the GL261 cells are stimulated by microglial-derived EGF. In xenograft studies, PLX3397 reduced the number of tumor-associated microglia and glioblastoma invasion (Figure 3).

**Figure 3: PLX3397 Inhibits Microglia/Macrophage Recruitment to GL261 Tumors in Vivo**

[figure not shown]

Note: Scale bar = 100 μm; \*p <0.001 compared with control)

Growing evidence in the literature suggests that macrophages and microglial cells are recruited by tumor cells as a resistance mechanism in response to radiotherapy (Ahn 2010). Accordingly, in subcutaneously implanted RM-1 syngeneic prostate cancer tumor cells, there is enhanced recruitment of both tumor associated macrophages (TAMs) and myeloid derived suppressor cells (MDSCs) after 5 days of irradiation. In this model, irradiation has a modest effect on tumor growth, and PLX3397 treatment has essentially no single agent effect. However, the combination provides highly synergistic tumor control as shown in Figure 4 (panel A). The relative resistance to irradiation appears to correlate with higher levels of TAMs (panels B, D) and MDSCs (panels C, E) in both tumor and spleen. PLX3397 substantially reduces levels of TAMs and MDSCs, and blockade of these cells likely leads to radiosensitization. These results along with ongoing

[figure not shown]
studies combining irradiation with PLX3397 in glioblastoma animal models strongly support the clinical evaluation of PLX3397 as a radiosensitizing anti-tumor agent.

**Figure 4: PLX3397 Inhibits RM-1 Tumor Regrowth After Irradiation in Vivo**

In a preliminary study, the radiosensitizing activity of PLX3397 has been explored directly in a mouse model of glioblastoma. In this model, U251 glioblastoma cells are implanted orthotopically within the cranium or nude mice. This study included 4 groups: (1) Control, (2) PLX3397 alone daily for 6 weeks, (3) Whole brain Irradiation with 12 Gy, and (4) Whole brain Irradiation with 12 Gy with PLX3397 given daily for 6 weeks starting the day of irradiation. As shown in Figure 5, the combination of PLX3397 with irradiation is clearly synergistic.

**Figure 5: PLX3397 Synergizes with Irradiation in the U251 Glioblastoma Model**

## 8.0 RATIONALE

As described above, there is a strong rationale for the use of a selective Fms inhibitor to decrease the role of activated microglia in GBM and to increase the efficacy of radiation and concurrent temozolomide. This study will provide an assessment of the safety and efficacy of PLX3397 added to standard radiation and temozolomide in patients with newly diagnosed GBM, compared to historical control data.

### 8.1 Route and Regimen

PLX3397 will be administered orally twice daily in capsule form at the dose described in [Section 13.13](#).

### 8.2 Treatment Period

There are 4 sequential periods: 1-week PLX3397 monotherapy; 6-week PLX3397/RT/TMZ combination therapy; 4-week recovery; and, PLX3397/TMZ adjuvant therapy. PLX3397 study drug will be administered twice daily either 7 days/week or 5 days/week (Monday through Friday) starting 1 week prior to the initiation of RT and will continue twice daily either 7 days/week or 5 days/week (Monday through Friday) during the 6-week course of RT. Four weeks after the completion of the course of RT, patients will be started on once-daily adjuvant temozolomide (Day 1-5 of a 28 day cycle) for up to 12 cycles as long as there is no disease progression or unacceptable toxicity and PLX3397 twice daily (28 days of a 28 day cycle) for as long as there is no disease progression or unacceptable toxicity.

## 9.0 OBJECTIVES

The study objectives are to assess the potential for PLX3397 to improve the efficacy of standard of care radiation therapy (RT) + temozolomide in patients with newly diagnosed glioblastoma (GBM). For Phase 1b dose escalation, the primary objective is identification of the recommended Phase 2 dose (RP2D). For Phase 2, the primary objective is the comparison of median Progression Free Survival (PFS) to historical control. Secondary objectives include the evaluation of overall survival (OS), pharmacokinetics (PK), correlative imaging studies, safety, and the exploratory endpoint of pharmacodynamic (PD) effects of PLX3397.

## 10.0 DESIGN

### 10.1 Description

This will be an open label, uncontrolled Phase 1b/2 trial in patients with newly diagnosed GBM who have recovered from complete or partial surgical resection. All patients will be treated with PLX3397 in addition to standard-of-care combination radiation therapy (RT) plus temozolomide (TMZ) followed by adjuvant TMZ. During Phase 1b dose escalation, two PLX3397 administration schedules, 7 days/week vs. 5 days/week (M-F) will be explored. During Phase 2, patients will be treated with the RP2D.

There are 4 sequential periods: 1-week PLX3397 monotherapy; 6-week PLX3397/RT/TMZ combination therapy; 4-week recovery; and, PLX3397/TMZ adjuvant therapy. PLX3397 will be administered twice daily either 7 days/week or 5 days/week (Monday through Friday) starting 1 week prior to the initiation of RT and will continue twice daily either 7 days/week or 5 days/week (Monday through Friday) during the 6-week course of RT.

Phase 1b PLX3397 dose and schedule cohorts are shown in [Table 2](#).

A detailed Trial Flow Chart is available in [Section 6.0](#), and procedures by study day are provided in [Section 13.0](#).

### 10.2 Number of Patients

For the Phase 1b portion of the study, 5 cohorts (2 cohorts from Amendment 1 and 3 from Amendment 2) are planned to be enrolled. Each cohort will consist of approximately 7 patients. Therefore, approximately 35 patients will be enrolled in Phase 1b. Additional patients may be required for replacement patients, or if lower dose cohorts (600 mg or 400 mg) are required. Phase 2 will enroll approximately 44 patients.

### 10.3 Number of Study Centers

The study will be performed at approximately 7-10 sites.

#### **10.4 Duration of Patient Participation**

Each patient will be offered continued dosing with PLX3397 and standard temozolomide up to 12 cycles of adjuvant treatment after radiation if this is well tolerated and there is no disease progression.

#### **10.5 Duration of Study**

The duration of the Phase 1b portion of the study will depend on the number of cohorts required and the need for replacement patients. For the Phase 2 portion of the study, a recruitment rate of 1 patient per site per month is anticipated. The total duration of enrollment is expected to be approximately 18 months. The duration of follow-up will depend on the prolongation of the median PFS; the study is powered to detect a median PFS of approximately 8 months.

### **11.0 SELECTION OF STUDY POPULATION**

All patients must participate in the consent process. During the consent process, the person obtaining consent must inform the patient of all elements of informed consent. No protocol-specific procedures, including screening procedures, are to be performed until the patient has signed and dated an institutional review board (IRB)/independent ethics committee (IEC)-approved informed consent form. The study begins with the signing and dating of the informed consent form. Patients must also meet the inclusion and exclusion criteria to be enrolled in the study.

#### **11.1 Inclusion Criteria**

1. Male or female patients  $\geq 18$  years old.
2. Histologically confirmed definitive GBM or gliosarcoma by partial or complete surgical resection (i.e. not by biopsy only) within 5 weeks prior to PLX3397 administration (C1D1). Tumor must have a supratentorial component. For all patients, availability of an archival paraffin tumor block sufficient to generate at least 20 unstained slides; or, if a paraffin tumor block is unavailable, at least 20 unstained slides.
3. The patient must have recovered from the effects of surgery, post-operative infection, and other complications before study registration.
  - a. A diagnostic contrast-enhanced MRI or CT scan of the brain must be performed preoperatively and postoperatively prior to the initiation of radiotherapy, i.e., within 28 days (14 days preferred) prior to study drug administration (C1D1).
  - b. Patients unable to undergo MR imaging because of non-compatible devices can be enrolled, provided pre- and post-operative contrast-enhanced CT scans are obtained and are of sufficient quality.
2. Patients must receive RT at the participating institution.

3. Women of child-bearing potential must have a negative pregnancy test within 14 days of initiation of dosing and must agree to use an acceptable method of birth control while on study drug and for 3 months after the last dose. Women of non-childbearing potential may be included if they are either surgically sterile or have been postmenopausal for  $\geq 1$  year. Men of child-bearing potential must also agree to use an acceptable method of birth control while on study drug, and for 3 months after the last dose.
4. Karnofsky performance status of  $\geq 70$ .
5. Adequate hematologic, hepatic, and renal function (absolute neutrophil count  $\geq 1.5 \times 10^9/L$ , Hgb  $> 10$  g/dL, platelet count  $\geq 100 \times 10^9/L$ , AST/ALT  $\leq 2.5 \times$  ULN, creatinine  $\leq 1.5 \times$  ULN).
6. Willing and able to provide written informed consent prior to any study related procedures and to comply with all study requirements.

### 11.2 Exclusion Criteria

1. Evidence of recurrent GBM or metastases detected outside of the cranial vault.
2. Investigational drug use within 28 days of the first dose of PLX3397 or concurrently.
3. Prior use of Gliadel wafers or any other intratumoral or intracavitary treatment.
4. Prior radiation or chemotherapy for glioblastoma or glioma.
5. Prior chemotherapy or radiosensitizers for cancer of the head and neck (except for T1 glottic cancer) that would result in an overlap of radiation fields.
6. Prior allergic reaction to temozolomide.
7. History of Grade 2 (CTCAE v4) or greater acute intracranial hemorrhage.
8. Active cancer (either concurrent or within the last 3 years) that requires non-surgical therapy (e.g. chemotherapy or radiation therapy), with the exception of surgically treated basal or squamous cell carcinoma of the skin, melanoma in-situ, or carcinoma in-situ of the cervix.
9. Chronic active hepatitis B or C.
10. Refractory nausea and vomiting, malabsorption, biliary shunt, or significant bowel resection that would preclude adequate absorption of study drug.
11. Patients with serious illnesses, uncontrolled infection, medical conditions, or other medical history including abnormal laboratory results, which in the investigator's opinion would be likely to interfere with a patient's participation in the study, or with the interpretation of the results.

12. Women of child-bearing potential who are pregnant or breast feeding.
13. At Screening QTcF  $\geq 450$  msec for males and  $\geq 470$  msec for females.

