--	--

	
12. Women of child-bearing potential who are pregnant or breast feeding.
 
13. At Screening QTcF <math>\geq 450</math> msec for males and <math>\geq 470</math> msec for females.

Dosage and Regimen	
Study drug will be administered orally using a capsule formulation (200 mg per capsule). The total daily dose of PLX3397 will be divided and administered BID. For an uneven number of capsules, the larger dose will be administered in the morning.
 
For Phase 1b PLX3397 dose and schedule cohorts and escalation, see Study Design (above).
 
The Phase 2 portion of the study will use the RP2D selected from the Phase 1b portion of the study.
 
As a part of standard of care, patients will receive the following:
 
 
• 60 Gy of radiation therapy Monday-Friday for a total of 30 radiation treatments over approximately 6 weeks.
 
• Temozolomide 75 mg/m^2 PO once daily for approximately 6 weeks beginning the first day of RT until RT end, followed by adjuvant treatment at a dose of 150 mg/m^2 once daily on Days 1-5 of the first 28 day cycle after completion of radiation therapy (start of Cycle 3). The dose can be escalated to 200 mg/m^2 if the non-hematologic toxicity is Grade <math>\leq 2</math> (except for alopecia, nausea, and vomiting), absolute neutrophil count (ANC) is <math>\geq 1.5 \times 10^9/L</math>, and the platelet count is <math>\geq 100 \times 10^9/L</math>.
 
• During the 4-week break after the completion of RT, neither temozolamide nor study drug will be administered.
 

Safety and Tolerability Assessments	
Physical examinations, vital signs, 12-lead ECGs, adverse events, hematology, and serum chemistry will be used to assess safety and tolerability.
 
As this is an open label study, ongoing safety will be continuously and rigorously monitored by the Sponsor. Additionally, biweekly teleconferences are planned to review in detail the safety across all study sites. Prior to dose escalation in the Phase 1b portion, safety data will be collated and reviewed by the Sponsor and study sites by teleconference.

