### **15.0 RADIATION THERAPY**

#### **15.1 Dose Specifications and Schedule**

Intensity Modulated RT (IMRT) is allowed, but the modality chosen at registration must be used for the entire course of treatment. Proton beam therapy is not allowed. For both IMRT and 3D-CRT plans, one treatment of 2 Gy will be given daily 5 days per week for a total of 60 Gy over

approximately 6 weeks. All portals shall be treated during each treatment session, for each course/sub-course of therapy, i.e. for the initial and boost phases. Doses are specified such that at least 95% of the Planning Target Volume (PTV) shall receive 100% of the prescribed dose; Dose Volume Histograms (DVHs) are necessary to make this selection.

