#### 15.4.4 Dose Limitations and Critical Structures

In addition to the above defined GTVs, CTVs and PTVs the lenses of both eyes, both retinae, both optic nerves, the optic chiasm, and the brainstem must be defined. The maximum point (defined as a volume greater than 0.03 cc) doses permissible to the structures are listed in the table below.

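### Exclusion 5 ties radiation-field overlap to drugs and does not name radiotherapy, so some earlier overlapping non-glioma radiotherapy is not expressly excluded before the 60 Gy course

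*Combined protocol and SAP*

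**What the plan says.** Four exclusions in Section 11.2, repeated in the synopsis, bear on earlier treatment or other cancers:

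- Item 3: "Prior use of Gliadel wafers or any other intratumoral or intracavitary treatment".
- Item 4: "Prior radiation or chemotherapy for glioblastoma or glioma".
- Item 5 bars "Prior chemotherapy or radiosensitizers for cancer of the head and neck (except for T1 glottic cancer) that would result in an overlap of radiation fields".
- Item 8: "Active cancer (either concurrent or within the last 3 years) that requires non-surgical therapy (e.g. chemotherapy or radiation therapy", with listed exceptions for some surgically treated tumours.

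Item 11 is a general clause. It lets the investigator exclude for serious illness, medical conditions "or other medical history including abnormal laboratory results" that in the investigator's opinion would interfere with participation or with interpretation of the results.

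On the study radiotherapy, Section 15.1 states that "one treatment of 2 Gy will be given daily 5 days per week for a total of 60 Gy", and the synopsis gives "60 Gy of radiation therapy Monday-Friday for a total of 30 radiation treatments". Section 15.4.4 says that the maximum point "doses permissible to the structures are listed in the table below", which is Table 6. Neither that section nor the planning rules in 15.4.1 to 15.4.3 mention radiation given before the study.

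**The concern.** In item 5 the overlap clause qualifies chemotherapy or radiosensitizers. Neither has a field, so the condition cannot be met by the treatments named. The exception for one early laryngeal tumour points the same way: it singles out a tumour by site and stage, which bears on where a field lies and not on which drug was given. The sentence evidently depends on radiotherapy but leaves it out. The synopsis has the same wording, so neither version corrects the other.

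What is at stake is safety. Field overlap is a hazard the sponsor set out to exclude, and the sentence written for that purpose does not do it when followed as written. At about 7 to 10 sites, investigators would have to choose between three readings: exclude nobody, exclude anyone with prior head-and-neck drug therapy, or exclude chemoradiation only. None of the three reaches head-and-neck radiotherapy given alone.

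**Working it through.** No significance level, power, event count or sample-size formula is involved. The check is to establish the study dose and then run concrete patient histories through every criterion that could apply.

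**Study dose.** From Section 15.1 and the synopsis: 30 fractions × 2 Gy = 60 Gy. From Section 15.4.3: 23 × 2 Gy = 46 Gy to the initial volume, plus 7 × 2 Gy = 14 Gy boost, and 46 + 14 = 60 Gy. The two descriptions agree.

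**Histories against exclusions 3, 4, 5, 8 and 11.** External-beam treatment is assumed, so item 3 does not apply.

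| Earlier radiotherapy, overlapping the study fields | Item 4 | Item 5 | Item 8 | What remains |
|---|---|---|---|---|
| For glioma | Excluded | – | – | – |
| For another cancer that was active and required radiotherapy within 3 years | No | – | Excluded | – |
| Head-and-neck chemoradiation, cancer not active within 3 years | No | Not as written; yes if read for its purpose | No | Item 11 if read literally |
| Head-and-neck radiotherapy alone, cancer not active within 3 years | No | No: no listed drug was given | No | Item 11 only |
| Cranial radiotherapy for another non-glioma cancer not active within 3 years | No | No: not head-and-neck cancer | No | Item 11 only |
| Cranial radiotherapy for a non-cancer condition, any time | No | No | No: not cancer | Item 11 only |

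The last three rows are the gap. It does not depend on reading item 5 strictly: even a generous reading does not reach radiotherapy given without a listed drug, or given for something other than head-and-neck cancer.

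**Other places that might close it.** The inclusion criteria (11.1) require radiotherapy at the participating institution but say nothing of earlier radiation. Screening (13.1) lists medical history without a specific prior-radiation item. Sections 15.3 to 15.5 require CT-based planning, definition of critical structures and dose-volume histograms, but not an account of earlier dose. Table 6 lists maximum doses by structure and does not say whether earlier dose counts towards them.

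**How many patients.** The documents give no frequency. Planned enrolment is about 35 in Phase 1b plus 37 newly enrolled in Phase 2, so 35 + 37 = 72. Assuming 0 to 2 such patients, the share is 0 to 2/72 = 2.8%. This range is an assumption, and its lower end is zero.

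**The case against.** The strongest defence is that a competent site would see what item 5 is for, since the overlap clause and the glottic exception both imply radiotherapy. Medical history is taken at screening, item 11 covers history that could affect participation or interpretation, and the radiation oncology team plans on CT with organs at risk outlined. A previously irradiated patient is therefore unlikely to go unnoticed. This stands in part. Read for its purpose, item 5 would still catch head-and-neck chemoradiation. But the other safeguards are discretionary or indirect, none mentions field overlap, and a general clause does not replace a specific criterion that the sponsor tried to write.

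A reader might also infer four stronger things that the documents do not support.

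- *That overlapping radiotherapy for any non-glioma disease is allowed.* Item 8 already excludes cancers at any site that were active and required radiotherapy within the last 3 years.
- *That Table 6 permits a particular cumulative dose.* The table is silent on earlier dose; it does not say that its limits apply to this course alone. A cumulative figure would need a prior dose found in no document and an assumption that old and new maxima fall at the same point.
- *That re-irradiation toxicity would distort the recommended Phase 2 dose.* Under Section 13.13.2 a non-hematologic DLT must be graded probably related to study drug. Section 23.1 reserves that grade for events not reasonably explained by the patient's clinical state, and grades as possibly related those that another therapy could have produced. The 11-week window ends 4 weeks after radiotherapy, while Section 15.6 places early delayed effects at 1 to 3 months and lists necrosis and visual damage as late. In the main, only a misattributed event would enter the count.
- *That the Phase 2 comparison is biased.* Whether the historical control trial (RTOG 0525) admitted such patients is not stated, and Section 21.4 plans matching on clinical and molecular factors.

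**Conclusion.** The concern holds in limited form. Exclusion 5 does not do what its own overlap clause shows it was meant to do. Earlier overlapping radiotherapy for non-glioma disease is not expressly excluded outside the 3-year window of exclusion 8; beyond that it rests on investigator opinion, ahead of 60 Gy, with no statement of how earlier dose counts. This follows from the text alone and needs no outside source.

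The size is small in numbers of patients, but the consequence for one affected patient could be irreversible. It is a patient-safety defect in an operative eligibility rule, not a threat shown to the dose decision or to the PFS analysis. The conclusion assumes that sites apply the criteria as written and that no separate site instruction, absent from these documents, supplies the missing term.

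**What to change.** Amend exclusion 5 in Section 11.2 and in the synopsis, in the same words, so that the overlap clause governs prior radiotherapy. If earlier head-and-neck chemotherapy or radiosensitizers are also meant to exclude, list them as a separate item without that clause.

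In the same amendment, reconcile exclusions 4, 5 and 8 with the 60 Gy plan, and state in Section 15.4.4 how earlier dose is to be treated against Table 6. The anatomical sites, indications, time limits and exceptions (including whether the glottic one stays) are clinical decisions for the sponsor. The documents do not settle them, and none is proposed here.

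The cost is one sentence in two places plus a short statement beside Table 6. The downside is the loss of a very few previously irradiated candidates.
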